Sample Size and Power Estimates. A provider group within the proposed study setting reported a 29.4% prevalence of GBS positive women among the 316 who gave birth in 2016. Therefore, we expect a 30% GBS prevalence in the placebo group compared to the probiotic group. To determine the effect size of the intervention, a sample of 80 women will be required to test the difference in proportions of GBS colonization and IAP between groups (hypotheses 1a and 1d). Hypotheses are unidirectional. With the sample size of 80 and setting alpha = 5%, one tailed test, 80% power estimate, and confounding variables (yogurt ingestion, vaginal cleansing practices, and sexual activity) accounting for multiple R-square = 0.1, we will be able to reject the null hypothesis for an effect size of Odds Ratio (OR) = 0.17 for the logistic regression to compare the proportion of GBS positives between groups. When comparing the colony counts (GBS and Lactobacillus) and GI symptoms (hypotheses 1b, 1c and 2), the same sample size = 80, power = 80%, alpha = 5%, one tailed test; we can reject the null hypothesis for a Cohen d = 0.56. This is a medium effect size, indicating that we can detect a difference between groups equivalent to 0.56 standard deviations. However, if the effect of the treatment is smaller we will be able to identify it, but not reject the null hypothesis of being equal to 0. This information is important for design of a full scale efficacy trial of the probiotic intervention. In our published preliminary study, 15 we found an overall dropout rate of 23%, but 30% in the probiotic group. For the proposed study, we chose a conservative 30% dropout rate to assure that the sample size can be fully achieved within the study timeline. Therefore, a total sample of 116 will be targeted for enrollment. Hypotheses 1b, 1c, and 2 will be tested by doing a multiple group comparison of the change in colony count for GBS and Lactobacillus, and the GI symptom inventory (M-SODA-9) scores [Section 2.3.1.8.e].

Recruitment. A sample of 116 women who meet the inclusion criteria, low-risk, healthy and pregnant, 26 ± 2 weeks gestation, 18 years of age, will be recruited from a population of central city maternity care recipients who see either certified nurse-midwives or physicians at the prenatal clinics of Aurora Sinai Medical Center (ASMC) in Milwaukee, Wisconsin. Approximately 200 new prenatal patients are seen monthly. **Inclusion and exclusion criteria are detailed in Table 1.**

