numbers, in an encrypted computer file, accessible only to the PI and the SC. The PI, co-investigators, SC, prenatal providers, and participants will be blind to group assignment. Data will be collected at five time points: T1 baseline (28 ± 2 weeks), T2 (36 ± 2 weeks), T3 (1-2 days post birth, before hospital discharge), T4 (2 weeks post birth phone call), and T5 (2 months post birth follow-up phone call). Measures and documentation tools appear in Appendices A through G. At each study visit, participants will be asked about any potential adverse events. Immediately following IC, participants will have their first study visit at 28 ± 2 weeks gestation (T1), during which baseline data will be collected and they will receive instructions to take one capsule by mouth daily until the time of birth. Also at T1 (28 ± 2 weeks), the participant will be seen by her prenatal provider, who will facilitate collection of the baseline study samples. Participants will be asked to collect their own vaginal and rectal swabs with assistance, but have the option of provider collection. This minimally invasive testing does not require a speculum exam. Self-collected swabs yield similar colonization measures compared to provider-collected, but may be more acceptable to women. 63,64 Each participant will also complete three brief questionnaires at T1. Vaginal and rectal swabs and 2 questionnaires will be collected at T2 (36 ± 2 weeks). At the end of T2, participants will receive a \$25 gift card. At T3, the SC will visit every participant on the postpartum hospital unit to administer two brief questionnaires, retrieve the study bottle with MEMS cap, and give a \$75 gift card. The SC will analyze the MEMS cap data, count and record the capsules remaining in the bottle, and conduct a chart review. At T4 and T5, the SC will text message the participants to indicate that she/he will be phoning the next business day. The following day, a phone call will be made to the participant to elicit any maternal and child health events (e.g., illness, antibiotics, or hospital readmission). At T5, the SC will also retrieve health records for the participant and her infant to examine them for the same maternal or child health events.

Table 2. Summary of Study Data Collection, Variables, Measures, and Timing

Outcome Variables	Study Data Collection	T1	T2	T3	T4	T5
	SC will document data from all measures on the Summary	28 ± 2	36 ± 2	1-2 days	2	2

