	Data Collection Form (SDCF; Appendix B).	weeks	weeks	post-	weeks	months
	See Appendixes A-G for data collection forms for all	baseline	prenatal	birth	post-	post-
	procedures.	visit	visit		birth	birth
	Procedures					
Qualitative GBS	Vaginal to rectal GBS swab. Collected at prenatal visit and	Not	X	Not		
Colonization (+ or -)	sends to hospital lab, results found in record	indicated		indicated		
Quantitative GBS Colony	Separate vaginal and rectal GBS swabs. Collected at	X	X			
Counts	prenatal visit and SC send to [name] lab					
Quantitative Lactobacillus	Separate vaginal and rectal Lactobacillus swabs. Collected	X	X			
Colony Counts	at prenatal visit and SC mailed to [name] lab					
Intervention Adherence	Vaginal and rectal swabs collected at prenatal visit		X			
	(presence of probiotic species verifies adherence)					
	2. MEMS™AARDEX™ wireless electronic cap counter ^{58,59}			Х		
	3. Final Pill Count			Х		
Maternal GI Symptoms	M-SODA-9 ^{65,66} GI symptom scale (completed by subject)	Х	Х	Х		
IAP	IAP doses based on qualitative GBS result; also SC			Х		
	records prenatal antibiotic exposures from medical record					
Demographics	Demographic characteristics Questionnaire	Χ				
Questionnaire for Women	Questionnaire on diet containing yogurt, sexual practices,	Χ	Х	X		
	vaginal cleaning practices (completed by study subject)					
Maternal-Infant Postbirth	SC interviews mother for maternal and infant health events	L	L	X		L
Health	and potential adverse events; documents			Х	TC	TC, HR
Adverse Events (AE)	Prenatal providers and SC solicit AE and document.		Х	Х	TC	TC, HR

Abbreviations: X = in-person study visit; TC = telephone call; HR = health record review.

- a. **Qualitative GBS Colonization.** Consistent with the CDC guidelines, between 35-37 weeks gestation (T2), the subject (or provider) will obtain a vaginal to rectal swab for GBS colonization to determine the need for IAP. [NOTE: In 2019, the guidelines changed and the prenatal GBS screens were collected at 36 weeks gestation.] The analysis of this swab will be done at the hospital laboratory and the result is reported as positive or negative for GBS. This swab will be done after the study swabs to prevent contamination of either site.
- b. **Quantitative GBS Colony Counts.** GBS colony counts, from separate vaginal and rectal swabs collected before the qualitative swabs, will be measured by [name] lab for this study, using CDC-recommended procedures to identify the number of GBS CFUs per swab (T1 & T2).

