 - c. Quantitative Lactobacillus Colony Counts. The swabs of vaginal and rectal sites will be analyzed to

identify the actual number of Lactobacilli in each area, counted as CFUs per swab (T1 &T2).

- d. Intervention Adherence Measures
- d.1. **PCR** and **16s** rRNA **Targeted Sequencing**. Vaginal and rectal swabs for PCR and 16s rRNA targeted sequencing will be collected (T2) by the participant or her provider and sent to [name] lab for analysis to detect the presence of the probiotic strains contained in the probiotic intervention group, verifying adherence.
- d.2. **MEMS Caps.** Each opening of the MEMS[™] AARDEX[™] wireless electronic cap counters^{58,59} will be recorded electronically with a software link to a study computer accessible to the SC and [name].
 - d.3. **Pill Counts.** The MEMS cap counts will be verified by the pill count when the bottle is returned.
- e. **Maternal GI Symptoms.** Because currently available GI quality of life scales focus on specific pathologies, we adapted the previously validated 7-item, non-pain symptom scale of the Severity of Dyspepsia Assessment (SODA)⁶⁵ (Cronbach's α = 0.9) to operationalize this variable. For use during pregnancy, the symptoms of "diarrhea" and "constipation" were added, resulting in a 9-item scale. Participants rate the severity of each symptom over the past week on a 6-point Likert scale, ranging from 0 = *no problem, not present* to 5 = *very severe problem, markedly influences daily activities and/or requires rest.* The score on the 9 items is summed to arrive at a GI symptom score ranging 0-45. Our **Ante-Partum Gastrointestinal Symptom Inventory (AP-GI-SA)** was validated in a pilot study with a sample of 45 healthy pregnant women. ⁶⁶ We found Cronbach's α = 0.84, test-retest reliability, stability, and content and face validity (T1, T2, and T3).
- f. IAP. If GBS-positive, the number and type of IAP doses will be recorded by SC on the **Summary Data Collection Form (SDCF).** Additional prenatal and intrapartum antibiotic exposures for participants and infants will be recorded on this form by the SC as potential cofounding variables.
 - g. Potentially cofounding variables
 - g.1. Participants will complete the brief **Demographic Questionnaire (DQ)** at T1 only.

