Confirmatory Factor Analysis: Aim 2. The GI symptom scale will be analyzed using a confirmatory factor analysis (CFA)⁷⁴ using R Version 3.3.1 or later.⁷⁵ With a multiple group CFA, we will compare the GI symptoms construct mean and variance between the placebo and treatment groups (hypothesis 2). Confounding variables will be included as covariates, estimating their effects for each group separately.

References

- 2. Centers for Disease Control and Prevention (CDC). Prevention of perinatal group B streptococcal disease. Revised guidelines from CDC. MMWR Morb Mortal Wkly Rep. 2002; 51(RR-11):1-22.
- 5. de Vrese M. Health benefits of probiotics and prebiotics in women. Menopause Int. 2009;15:35.
- 6. Bizzarro MJ, Dembry L-M, Baltimore RS, Gallagher PG. Changing patterns in neonatal Escherichia coli sepsis and ampicillin resistance in the era of intrapartum antibiotic prophylaxis. Pediatrics. 2008;121:689-696.

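### Hypothesis 2 (GI symptoms): the factor-analysis test names no visit and no baseline term; specify one post-randomisation visit, adjusted for the T1 score already collected

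*Combined protocol and SAP*

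**What the plan says.** All references are to the combined protocol and SAP.

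- **Confirmatory Factor Analysis: Aim 2.** The test of hypothesis 2 is given as "With a multiple group CFA, we will compare the GI symptoms construct mean and variance between the placebo and treatment groups (hypothesis 2". On covariates: "Confounding variables will be included as covariates, estimating their effects for each group separately". The section gives no visit, no T1 GI term, and neither a visit nor a reference value for the covariates.
- **Table 2 and item e (Maternal GI Symptoms).** The "GI symptom scale (completed by subject") is marked at T1, T2 and T3. On scoring: "The score on the 9 items is summed to arrive at a GI symptom score ranging 0-45". At T3, under Procedure and Timing, "the SC will visit every participant on the postpartum hospital unit to administer two brief questionnaires".
- **Item g.2.** The questionnaire on yogurt, vaginal cleansing and sexual activity is also completed at T1, T2 and T3. Item f and Descriptive Analyses add prenatal antibiotic use as a possible confounder.
- **Sample Size and Power Estimates.** Hypotheses 1b, 1c and 2 are to be tested by a "multiple group comparison of the change in colony count for GBS and Lactobacillus, and the GI symptom inventory (M-SODA-9) scores". For 80 women, one-tailed 5% and 80% power, "we can reject the null hypothesis for a Cohen d = 0.56". On the preliminary study: "we found an overall dropout rate of 23%, but 30% in the probiotic group".
- **Plan for Missing Data.** A likelihood-based repeated-measures analysis is promised that keeps all randomised women and all available data.
- **Continuous Outcomes Analyses: Aims 1 and 2.** Despite its heading, the T1-to-T2 mixed model is specified only for the two colony counts (hypotheses 1b and 1c).

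**The concern.** Three sections bear on hypothesis 2 and they describe different analyses. One describes a between-arm comparison of a construct mean with no time element. One may describe a comparison of change. One promises a repeated-measures likelihood model.

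This leaves open which visit carries the test, how T1 enters, and which covariate values are used. The last matters because questionnaire answers at T2 and T3 come after randomisation and could be affected by treatment.

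At stake is precision, and having a single test fixed in advance. The T1 score is collected anyway. Leaving it out gives up power, and a change score can do worse than leaving it out. A factor analysis of one later visit with no T1 term would also make no use of the T1 score of a woman who misses that visit, contrary to the missing-data section. Hypothesis 2 is not the main hypothesis, so the primary conclusion does not depend on this.

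**Working it through.** **Inputs from the plan:** 80 evaluable women, taken as 40 per arm from the 58/58 bottle allocation; one-sided alpha 5%; d = 0.56; 30% dropout; 116 enrolled. **Assumed:** correlation r between the T1 and follow-up GI scores of 0.3, 0.5 and 0.7, because the documents give none.

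**1. The plan's own figure.** For an unadjusted two-sample t test the noncentrality is d × √(n/2) = 0.56 × √20 = 2.504. With 78 df the one-sided critical value is 1.665, and power is 79.9%. The difference detectable with 80% power is 0.561 SD. For enrolment, 40/0.7 = 57.1, rounded up to 58 per arm, or 116. Both figures reproduce. The stated 0.56 is therefore a single-time comparison that uses no T1 information.

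**2. Adding T1.** Adjusting for T1 multiplies the residual SD by √(1 − r²), with 77 df. A change score multiplies it by √(2(1 − r)), with 78 df. Each factor divides 0.56 to give the effective d, and multiplies 0.561 to give the detectable d.

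| | r = 0.3 | r = 0.5 | r = 0.7 |
|---|---|---|---|
| No T1 term: power | 79.9% | 79.9% | 79.9% |
| T1-adjusted: SD factor | 0.954 | 0.866 | 0.714 |
| T1-adjusted: effective d | 0.587 | 0.647 | 0.784 |
| T1-adjusted: power | 83.1% | 88.9% | 96.6% |
| T1-adjusted: detectable d | 0.535 | 0.486 | 0.401 |
| Change score: SD factor | 1.183 | 1.000 | 0.775 |
| Change score: effective d | 0.473 | 0.560 | 0.723 |
| Change score: power | 67.5% | 79.9% | 94.1% |
| Change score: detectable d | 0.664 | 0.561 | 0.434 |

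The change score loses to ignoring T1 when r is below 0.5. T1 adjustment is the most precise of the three at each of these correlations. With T1 adjustment, 80 × (1 − r²) = 73, 60 and 41 women give the precision of 80 unadjusted women.

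**3. Does this carry over to a factor model?** A simulation used nine normal items, one factor, reliability 0.84 (the plan's Cronbach's alpha), arm-specific slopes and centred covariates, with 1,000 runs per setting. Power was 80/83/84% without T1 and 86/90/98% with T1 at the same three correlations. Type I error in that simulation was 6.0% to 6.7%, so these powers are slightly flattering, and skewed 0–5 items were not simulated. The pattern matches the table.

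**4. Why name the visit.** If T2 and T3 were both tested at one-sided 5% and the better one reported, the chance of a false positive would be 9.3%, 8.8% and 8.1% for correlations of 0.3, 0.5 and 0.7 between the two tests. The plan does not say that this would be done, but it does not exclude it.

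**5. Why state the covariate value.** With arm-specific slopes, the arm difference at covariate value x is the difference in intercepts plus x times the difference in slopes. The contrast is undefined until x is fixed. Centring at the pooled mean fixes it at the average woman.

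**The case against.** The best defence is that T1 is not shown to be ignored. The sample-size wording can naturally be read as change in the GI score, the missing-data section commits to repeated measures, and the text cited for the factor analysis concerns longitudinal models. This defence stands in part. The defect is that the sections are not aligned, not that the sponsor is proved to discard T1. But the word for change may attach only to the colony counts, it names no visit, and the mixed model covers only 1b and 1c, so none of this settles the test.

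Two stronger readings are tempting.

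- **Inflated type I error.** A reader might infer false-positive rates of about 9% to 15%. Those arise in a simulation that analyses only women with a T2 score and lets dropout odds double per SD of T1 score in the probiotic arm alone. The missing-data section does not commit to such a completer analysis. The preliminary study shows unequal dropout, not dropout related to T1 symptoms. When dropout is unrelated to T1, the same simulation gives 5.1% to 5.5%.
- **Collapsed power.** A reader might infer power near 31% from arm-specific slopes. That requires intercepts compared at zero covariates, which the plan does not state, and invented covariate means. Other assumed values give anything from 23% to 72%.

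It is also fair that the choice between T2 and T3 is a judgement. T2 is the colony-count visit, and the past-week recall at T3 takes in labour and birth. Yet capsules continue until labour, so T3 is the only GI assessment after the full course.

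**Conclusion.** The point holds as a modest, recommended clarification with a real gain in precision. The section defining the hypothesis 2 test gives no visit and no T1 term, and the sample-size and missing-data sections do not fill the gap consistently.

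The size rests on assumed correlations and a t-test approximation to the factor model. T1 adjustment adds about 3, 9 and 17 percentage points of power over no T1 term at r = 0.3, 0.5 and 0.7. Over a change score it adds about 16, 9 and 3 points (differences taken from the table).

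Omitting T1 mainly costs precision and does not itself bias a randomised comparison. Including it would also protect against bias if dropout were related to T1 symptoms, but the documents do not show that it is. The factor analysis, the arm-specific slopes, N and the unadjusted d = 0.56 are not errors, and the primary conclusion is unaffected.

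**What to change.** In Confirmatory Factor Analysis: Aim 2, state that:

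1. Hypothesis 2 is tested as the between-arm difference in the GI construct at one named post-randomisation visit. The sponsor chooses T2 or T3, and the other visit is supportive.
2. The T1 GI construct or the T1 score (say which) is in the same likelihood model, so that women who miss the named visit are retained, as the missing-data section requires.
3. Yogurt, cleansing and sexual activity enter at their T1 values, centred at the pooled mean if slopes stay arm-specific.
4. For prenatal antibiotic use, only exposure before randomisation is adjusted for.

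Then align the sample-size, missing-data and factor-analysis sections with this, and label d = 0.56 as the unadjusted two-sample figure.

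The cost is SAP wording only. The T1 score and T1 questionnaire are already collected, and N does not change. The downsides are a small gain if the correlation is near 0.3, one visit reduced to a supportive role, and reliance on missingness depending only on observed data.
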